Principal Investigator: [name]
Application Number: IRB00242136
NCT# NCT04290988
Study Title: Circuitry Assessment and Reinforcement Training Effects on Recovery (CARTER)

intervention phase regarding their best-guess as to which type of intervention they are receiving (active versus sham) to assist in determining if they are adequately blinded.

d. Justification of why participants will not receive routine care or will have current therapy stopped.

Participation in this study will not disrupt any current care or therapy. If participants are actively undergoing regular speech therapy while enrolled in this study, we will record the amount of outside speech therapy participants receive during each intervention phase (in terms of number of speech therapy visits and duration of these visits, e.g., 60-minutes) during each intervention phase.

e. Justification for inclusion of a placebo or non-treatment group.

All participants will be participants who will undergo active and sham conditions, thus serving as their own control.

f. Definition of treatment failure or participant removal criteria.

Participants will be removed from the study if they are unable to comply with task instructions or tolerate the EEG neurofeedback, measured by self-report or overt signs of discomfort.

g. Description of what happens to participants receiving therapy when study ends or if a participant's participation in the study ends prematurely.

When the study ends participants will continue to receive management with [name] or their own neurologist as usual (generally follow-up visits every about 6 months). If a patient's participation in the study ends prematurely s/he will still receive care as before. In sum, termination of the study or termination of participation in it will not affect regular treatment he or she may be receiving.

5. Inclusion/Exclusion Criteria

Participants in this study will have a diagnosis of Primary Progressive Aphasia or aphasia following stroke. Diagnostic evaluations will be conducted during the participants' initial visit to confirm aphasia diagnosis.

Inclusion Criteria:

- 1) Diagnosis of PPA or aphasia secondary to stroke and presence of naming deficits with confirmation of diagnosis by neurologist
- 2) Capable of giving informed consent or indicating another to provide informed consent
- 3) Age 18 or older.

Date: November 11, 2021
Principal Investigator: [name]
Application Number: IRB00242136
NCT# NCT04290988

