The primary outcome variable will be the change in number of Content Units (CU) in picture description from baseline to 1-week post-treatment. Hypothesis 1A is: Participants will show greater improvement in CU from baseline to 1-week post treatment, during the EEG neurofeedback condition than during the sham condition.

To test Hypothesis 1A, we will subtract baseline CU from 1-week post-treatment CU, for each condition. We will use a paired t-test to determine if, as a group, patients showed greater increase in CU during the neurofeedback condition compared to the sham condition. We will also carry out paired t-tests for post-stroke aphasia and PPA separately, to determine if the effect was greater in one group.

b. Secondary outcome variables

Hypothesis 1B-F take the form of: Participants will show greater improvement in [outcome variable] from baseline to 1-week post treatment, during the EEG neurofeedback condition than during the sham condition.

To test each hypothesis 1B-F, we will subtract baseline score from follow up scores (1-week post-treatment), for each condition. We will use paired t-tests to determine if, as a group, patients showed greater improvement during the neurofeedback condition compared to the sham condition, at each follow-up. We will correct for multiple comparisons using a Bonferroni correction.

Hypothesis 2A is: We will be able to identify baseline characteristics (demographics and baseline severity measures, as well as qEEG abnormalities) that influence change in the primary outcome measure (change in CU in picture description from baseline to 1-week post-treatment).

To test this hypothesis, we will carry out multivariable linear regression, with the dependent variable (change in CU in picture description from baseline to 1-week post-treatment), and independent variables of age, baseline CU, baseline OANB, baseline COWA, baseline sleep quality, baseline S-anxiety (STAI), brainwave activity (absolute power, peak amplitude frequency) in each frequency band (alpha, beta, theta, delta, gamma) on qEEG.

Hypothesis 2B is: We will be able to identify changes in secondary outcome measures and changes in qEEG that correlate with the primary outcome measure (change in CU from baseline to 1-week post-treatment). These results will allow us to identify variables to explore the mechanisms of the effects.

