To test this hypothesis, we will compare baseline and follow-up z-scores for coherence in each of the frequency bands (alpha, beta, theta, delta, gamma) by subtracting the absolute value baseline z-score from the absolute value follow-up z-scores for coherence in each condition. We will use paired t-tests to determine if, as a group, patients showed greater improvement during the neurofeedback condition compared to the sham condition, at each follow-up. We will correct for multiple comparisons using a Bonferroni correction. We will also carry out paired t-tests for post-stroke aphasia and PPA separately, to determine if the effect was greater in one group.

c. Statistical plan including sample size justification and interim data analysis

Statistical Analyses

Statistical tests to evaluate each hypothesis are described above. No interim data analyses are planned, although we will become unmasked to condition after each participant completes the 5 week follow-up

Sample Size Determination

This study is a novel application of neurofeedback for treatment of aphasia, and we have no preliminary data to guide a power analysis. However, we will use this preliminary cross-over study (with each patient as their own control) to identify effect size (if any), in order to plan a randomized, double-blind, parallel, sham-controlled trial. For this preliminary trial, we plan to study 8 patients per year with post-stroke aphasia, and 8 patients per year with PPA, based on our other ongoing trials of post-stroke aphasia and PPA, in which we have found that it is feasible to recruit and retain 8-10 of each per year. We hope to obtain a total of 40 patients with post-stroke aphasia and 40 with PPA over 5 years, to obtain preliminary data for a multicenter, randomized, double-blind, parallel, sham-controlled trial, if the preliminary results are positive.

Missing Data

We plan to minimize missing data by avoiding prolonged intervals between conditions. Most of the study will take place within 7-11 weeks, with each person scheduled to have a 5 week follow up to determine if any changes are long-lasting. To minimize biases, analyses will be by

Date: November 11, 2021
Principal Investigator: [name]
Application Number: IRB00242136
NCT# NCT04290988
Study Title: Circuitry Assessment and Reinforcement Training Effects on Recovery (CARTER)

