intention to treat; any missing data will be addressed with the technique of multiple imputation (Rubin, 2004), generally recognized as best for handling missing data (Little et al., 2012).

d. Early stopping rules.

N/A

8. Risks

a. Medical risks, listing all procedures, their major and minor risks and expected frequency.

Two primary instrumental techniques will be utilized, EEG and fNIRS, neither of which have major risks associated. Since EEG neurofeedback is a passive learning process, there is a limit to the extent of negative reactions that can arise as a result of its use (Collura, 2014). Collura discusses two types of abreactions (expression and consequent release of a previously repressed emotion) that might occur as the brain learns self-regulation and normalizes through neurofeedback training. One type of such reactions could be if neurofeedback training results in normalization of a compensatory mechanism that has helped the client cope with particular stresses or other dysregulations. An example could be if a chronically anxious client exhibits excess alpha as a coping mechanism to reduce anxiety. If through neurofeedback training, alpha levels normalize and reduce this coping mechanism, anxiety levels could increase. The long-term goal of neurofeedback is to allow the client to develop healthier circuitry patterns that do not rely on maladaptive patterns in order to cope. The second type of possible abreaction could be the resurfacing of psychological trauma that had been dealt with through coping mechanisms once these coping mechanisms are lessened through more normalized brainwave activity. Another possible negative response is the development of negative effects from current medication regimens as the trainee's brain learns to self-regulate and normalize.

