Participants will be carefully screened prior to being scheduled, to assure that they meet study criteria. EEG neurofeedback sessions will be closely supervised to monitor for any adverse reactions. The participant may stop testing or the intervention at any time. On any given session, if the patient experiences significant frustration, anxiety, or fatigue, that session may be terminated early. Short-term abreaktions will be monitored closely. Those with a history of severe psychological trauma and severe psychological conditions will be excluded from the study.

In the event of a global pandemic (such as COVID-19 outbreak), precautions will be taken to reduce the spread of infection related to the viral outbreak. This includes the following:

1. Remote testing will become the primary mode of testing.
2. If remote testing is not feasible, we will perform home visits whenever possible to limit contact of participants with others at the hospital setting.
3. We also have the option of using the STAR Car, a mobile lab space (wheelchair-accessible van) to reduce the number of people on-campus.
4. If remote testing and/or home visits are not possible, participants may be seen at their outpatient appointment scheduled for clinical follow-up.
 - a. For outpatient appointments, we will limit session room attendance to the participants only (rather than allowing family members to be present in the testing room) and one staff member to administer the session.
 - b. We will also limit lab staff members on-site to essential personnel only, per JHU guidelines.
5. We will screen participants by phone to inquire about recent symptoms and exposure to (e.g., related to COVID-19) before any in-person appointments. Per JHU guidelines, we will defer any appointments (i.e., if any active symptoms are present, we will defer any in-person appointments).
6. Staff will reference JHU policies for self-screening and will defer any in-person or on-campus activities if they suspect that they have any active symptoms (e.g., related to COVID-19).
7. For all in-person visits, we will disinfect test and treatment materials (computers, caps, tablets, pens), devices (EEG amplifier, electrode leads, fNIRS system, optodes) and surfaces (tables, doorknobs) before and after each session.

Date: November 11, 2021
Principal Investigator: [name]
Application Number: IRB00242136
NCT# NCT04290988
Study Title: Circuitry Assessment and Reinforcement Training Effects on Recovery (CARTER)

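### Section 4f takes people who cannot comply with or tolerate neurofeedback out of the study, not only out of training, so some measurable primary outcomes would be imputed

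*Combined protocol and SAP*

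**What the plan says.** - **Section 4f (removal criteria):** "Participants will be removed from the study if they are unable to comply with task instructions or tolerate the EEG neurofeedback". Intolerance is "measured by self-report or overt signs of discomfort". The section does not say who decides.
- **Section 4g (premature end):** the only provision is clinical. If a patient's "participation in the study ends prematurely s/he will still receive care as before". No outcome visit is mentioned.
- **Section 4a (visit schedule):** behavioural outcomes are measured at Visit 1, Visit 18 (one week after Phase I), Visit 34 (one week after Phase II) and Visit 35 (five weeks after Phase II). There is no early-termination or off-treatment visit.
- **Section 7a (primary analysis):** change in CU is computed for each condition, then "We will use a paired t-test to determine if, as a group, patients showed greater increase in CU during the neurofeedback condition", compared with sham.
- **Section 7c (missing data):** the only preventive step is to keep the interval between conditions short. Analyses are by "intention to treat; any missing data will be addressed with the technique of multiple imputation". No imputation model, missingness assumption or sensitivity analysis is given.
- **Section 8b (minimising risk):** "The participant may stop testing or the intervention at any time", and on a given day, "if the patient experiences significant frustration, anxiety, or fatigue, that session may be terminated early".

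**The concern.** In a crossover trial with a paired primary test, each participant's contribution depends on being assessed after both periods. A rule that ends study participation whenever training cannot be continued turns a treatment problem into a missing-data problem. Intention to treat is best served by measuring the outcome. Imputation is a fallback that relies on an assumption the data cannot test.

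The trigger makes this more than a loss of precision. Removal depends on how the person reacts to training or on whether they can follow instructions, and either could be related to the change in CU that would have been seen. Section 8a describes possible reactions to neurofeedback such as increased anxiety. In aphasia, the ability to follow instructions may track the language ability being measured. The study's stated purpose is to identify an effect size for a later parallel trial, so any bias would carry into that trial's planning.

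**Working it through.** **1. The plan's own figure.** Section 7c plans 8 patients per year in each diagnosis for 5 years: 8 × 5 = 40 per diagnosis, and 2 × 40 = 80. The stated total reproduces. The section gives no SD, power calculation, expected removal rate or allowance for loss, so every size below rests on assumed inputs.

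**2. What removal costs under the plan as written.**

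| Removal during | Phase I change | Phase II change | Paired difference |
|---|---|---|---|
| Phase I (before Visit 18) | not observed | not observed | not observed |
| Phase II (after Visit 18) | observed | not observed | not observed |

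**3. What continued assessment could recover.**

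- *Stops in Phase II for intolerance.* The Phase I change is already in hand. Attending Visit 34 completes the pair, as a treatment-policy outcome.
- *Stops in Phase I but is willing and able to start Phase II.* Attending Visits 18 and 34 gives both changes.
- *Stops in Phase I and never starts Phase II.* Visit 34 then reflects neither active nor sham training, so no active-sham contrast is recovered.
- *Cannot follow instructions.* Picture description may be unusable whether or not the visit takes place.

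The recoverable part is therefore the first two groups. The documents do not allow their number to be computed.

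**4. Size of a possible bias.** Units are SDs of the active-minus-sham difference. Let f be the share removed and d the amount by which the removed participants' true mean difference falls short of the values imputed for them. Then, by definition, bias = f × d.

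| Assumed f (of 80) | d = 0.25 | d = 0.5 | d = 1.0 |
|---|---|---|---|
| 5% (4 people) | 0.0125 | 0.025 | 0.05 |
| 10% (8 people) | 0.025 | 0.05 | 0.10 |
| 20% (16 people) | 0.05 | 0.10 | 0.20 |

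The sign follows d. If removed participants would have done better than their imputed values, the bias is reversed.

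**5. Yardstick.** The 95% half-width is t(0.975, n − 1)/√n. With 80 pairs it is 0.2225. Using complete pairs only, it is 0.2285 with 76, 0.2350 with 72 and 0.2498 with 64. The middle case, 0.05 SD, is 0.05 × √80 = 0.45 standard errors. The extreme corner, 0.20 SD, is 0.20 × √80 = 1.79 standard errors, but it needs both 20% removal and a full 1 SD unexplained shortfall.

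**6. What a delta-adjusted analysis would show.** Shifting the imputed differences by ±1 SD moves the estimate by 4/80 × 1 = ±0.05 SD with 4 imputed, and by 16/80 × 1 = ±0.20 SD with 16 imputed.

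**The case against.** The strongest reply is that the plan already covers this. It commits to intention to treat and multiple imputation. Section 8b mentions testing and the intervention separately and lets a single session end early without ending participation. No text forbids a later assessment, so 4f may simply be loosely worded. Part of this stands. A reader might infer that 4f contradicts the intention-to-treat statement, and it does not, because imputation keeps removed people in the analysis set. But 8b covers stops that participants choose and the ending of single sessions. It schedules nothing after removal and does not override 4f.

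Three stronger readings also go beyond the documents.

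- *Removal is informative and biases the result.* The trigger makes this plausible, but nothing shows it. The rule applies in both active and sham periods, and section 6a calls the risks minimal. One can simulate substantial bias and an inflated type I error by concentrating Phase II removals in one sequence among people with a low Phase I change. A negative bias of that kind arises only if the whole paired difference is imputed and the Phase I change observed at Visit 18 is discarded. Putting that change in the imputation model removes the bias with no extra visits. Such an exercise argues for naming the imputation variables, not for continued assessment.
- *All the missing pairs are avoidable.* They are not, for the two groups set out in step 3 of the working.
- *Retention is known to be good, or known to be a problem.* Section 7c says "we have found that it is feasible to recruit and retain 8-10 of each per year". That is a count from other trials, not a rate. Since 8 per year are planned, 80 may already allow for losses.

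**Conclusion.** The point holds in a limited form. Following 4f as written ends outcome collection for people who cannot comply with or tolerate neurofeedback. Some primary outcomes that could have been measured would then be imputed, although the plan states intention to treat. The number affected and the direction of any bias are unknown. An assumed 10% removal with a 0.5 SD unexplained shortfall gives a bias of 0.05 SD, less than a quarter of the 0.2225 SD half-width with 80 pairs. Over the assumed ranges of 5–20% and 0.25–1.0 SD, the bias runs from about 0.01 to 0.20 SD, and the documents do not say where in that range the trial would fall. This is a low-cost improvement to a preliminary study, not a defect that invalidates its analysis.

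**What to change.** **Section 4f.** State that stopping training in a period is not leaving the study. Invite participants who stop and still consent to the behavioural assessments at Visits 18, 34 and 35 on schedule, with qEEG and fNIRS optional. Let someone who stops in Phase I start Phase II if willing and able. Say whether VNeST continues, since it is delivered in the same sessions. Record the reason for stopping and its timing, and keep both from the blinded assessors.

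**Section 7c.** Analyse by randomised sequence. Impute only the period change that is missing, with sequence, diagnosis, baseline scores (CU, OANB, COWA, PSQI, STAI) and any observed Phase I change in the model. Add a delta-adjusted sensitivity analysis defined on the active-minus-sham scale, for example shifting imputed differences from −1.0 to +1.0 SD.

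**Cost.** A few sentences, and up to three already scheduled behavioural visits for each person who stops, any of whom may decline. Testing burden rises slightly. Some participants will still be untestable, and a Phase I stopper who does not start Phase II still gives no active-sham contrast. The resulting treatment-policy estimate is not the on-treatment contrast, and the report should say so.

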Study Title: Circuitry Assessment and Reinforcement Training Effects on Recovery (CARTER)

either an active EEG neurofeedback intervention period first followed by a sham intervention period, or a sham intervention period first followed by an active EEG neurofeedback intervention period. Participants will receive 15 training sessions within the active EEG neurofeedback intervention period and 15 sessions within the sham intervention period. Each participant will receive 2-5 sessions per week depending on their preference and availability. All participants will receive traditional behavioral speech-language therapy while simultaneously undergoing active or sham neurofeedback. Speech-language therapy will be performed within the same session as the active/sham neurofeedback training. The EEG neurofeedback and sham intervention periods will be separated by a 1 week “wash out period”. Communication will be evaluated before therapy and again in the week immediately following therapy, for each intervention period.

To evaluate the effects of EEG neurofeedback on communication skills in participants with post-stroke aphasia and PPA, we will carry out a randomized double-blind, sham controlled, within-subject crossover trial design. The Object Action Naming Battery (OANB) (Druks, 2000) will be used to evaluate communication skills by testing participants at baseline and in the week immediately following treatment. The primary outcome variable will be the change in number of Content Units (CU) in picture description, because this measure is a sensitive measure of communication impairment in both left and right hemisphere stroke (Agis et al., 2016) and PPA (Berube & Hillis, 2019). Secondary outcome variables will be change in accuracy of naming on the OANB, change in number of words produced on the Controlled Oral Word Association test (COWA, a measure of attention, executive function, and word-retrieval), change in quality of sleep measured with The Pittsburgh Sleep Quality Index (PSQI), change in anxiety measured with State Trait Anxiety Inventory, and change in frequency of use of sleep medications.

Hypothesis 1A. Participants will show greater improvement in correct CU in picture description from baseline to 1-week post treatment, during the EEG neurofeedback condition than during the sham condition.

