In the past few decades, analysis of EEG recording has become more sophisticated, with the discovery of "source analysis." EEG signals can instantaneously perceive electrical current variations in the brain. Real-time EEG applications such as neurofeedback and brain-computer interfaces that capitalize on the high-temporal resolution of EEG have become an area of interest for potential clinical applications. The most direct method for using qEEG information to guide

Date: November 11, 2021
Principal Investigator: [name]
Application Number: IRB00242136
NCT# NCT04290988
Study Title: Circuitry Assessment and Reinforcement Training Effects on Recovery (CARTER)

neurofeedback training utilizes training protocols based on z-score deviation for a specific feature. This is called live z-score training (Johnstone & Lunt, 2011).

This study aims to investigate what behavioral and physiological changes can occur in individuals with communication impairments when we reinforce healthier circuitry by reinforcing improved synchronous firing patterns (e.g. enhanced alpha) through EEG biofeedback. There is accumulating literature suggesting that there is value in using EEG information for guiding clinical intervention with medication and neurofeedback (Johnstone & Lunt, 2011).

Since neurofeedback is a learning technique, it has potential for intrinsically lasting effects. Collura (2014) proposed that these “brain exercises” have potential to implement changes that produce the desired feedback and increase self-regulation. Collura hypothesized possible mechanisms of EEG neurofeedback training to include changes in cortical excitability, generation and uptake of neurotransmitters, and cortical and subcortical connectivity. Trainees may benefit from physiological and behavioral changes. Physiological changes may be validated by repeated qEEG assessment, and behavioral changes can be measured through neuropsychological testing.

Since behavioral training is based on principles of neuroplasticity, operant conditioning, and learning principles, it is possible that this type of network-level skill learning could increase recruitment of novel pathways in PPA and in stroke recovery and strengthen current neural network pathways. This modality could also maximize brain regulation to support efficient brain activity for creation of novel pathways during neurorehabilitation. Results of this study could inform future work in behavioral interventions in neurorehabilitation.

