We will offer Verb Network Strengthening Treatment (VNeST) in conjunction with EEG biofeedback (i.e., neurofeedback) to test our hypothesis. VNeST has been shown to improve

Date: November 11, 2021
Principal Investigator: [name]
Application Number: IRB00242136
NCT# NCT04290988
Study Title: Circuitry Assessment and Reinforcement Training Effects on Recovery (CARTER)

[figure not shown]
language skills, especially verb naming skills (Edmonds, 2016; Edmonds & Babb, 2011; Edmonds, Mammino, & Ojeda, 2014; Edmonds, Nadeau, & Kiran, 2009; Furnas & Edmonds, 2014). Since VNeST targets verb naming skills, we will also change our language assessment and primary outcome measure from the *Philadelphia Naming Test* (PNT; which assesses noun naming skills) to the *Object and Action Naming Battery* (OANB; (Druks, 2000). The OANB is a validated language measurement tool which assesses both noun and verb naming skills. It will be especially important for us to assess participants' change in verb naming skills pre- and post-intervention since our language intervention targets verb-naming skills.

4. Study Procedures

a. Study design, including the sequence and timing of study procedures (distinguish research procedures from those that are part of routine care).

Study Procedures

Study Design Overview: Participants will take part in two intervention periods of 15 training sessions (2-5 per week), with either neurofeedback training or sham training, separated by a 1-week wash-out period. At each training session, participants will also receive 45 minutes of speech-language therapy (VNeST). Behavioral speech-language testing and physiological testing (qEEG and fNIRS) will be conducted at baseline, at 1-week following each intervention period and at five weeks following the completion of both conditions. See the figure below. In order to effectively analyze and code errors in the participant's speech/language, we will perform audio and/or video recordings of their behavioral language testing. All recordings will be accessed via JHU SAFE Desktop and stored on JHU HIPAA-compliant network drives.

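### Section 7a tests the two-period crossover without a period term, and the plan reports nothing that would show whether a fading or growing phase I gain distorts the planning effect size

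*Combined protocol and SAP*

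**What the plan says.** Section 7a forms a change score per condition: "To test Hypothesis 1A, we will subtract baseline CU from 1-week post-treatment CU, for each condition". The two scores are then compared: "We will use a paired t-test to determine if, as a group, patients showed greater increase in CU during the neurofeedback condition" than during sham. The same test is used by diagnosis: "We will also carry out paired t-tests for post-stroke aphasia and PPA separately, to determine if the effect was greater in one group". Sections 7b and 7c add no period or sequence term, mixed model or sensitivity analysis for this outcome.

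The design offers three protections: randomised order, a 1-week washout, and an assessment around each phase (section 2: "Communication will be evaluated before therapy and again in the week immediately following therapy, for each intervention period"). Section 4a adds: "Behavioral speech-language testing and physiological testing (qEEG and fNIRS) will be conducted at baseline, at 1-week following each intervention period". Visit 1 is labelled the baseline for the first phase. Visit 18, one week after phase I, is the only assessment listed between phases. Section 7a does not say which visit is the phase II baseline. The design figure is not available to us and may do so.

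Under Sample Size Determination in section 7c, the trial's purpose is to supply an effect size for a later parallel-group sham-controlled trial.

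**The concern.** Phase I and phase II gains need not be equal. Section 2 states: "All participants will receive traditional behavioral speech-language therapy while simultaneously undergoing active or sham neurofeedback". Therapy gains may therefore differ between the first and second block of 15 sessions, and half the planned sample has a progressive disease. An unadjusted paired t-test puts any such difference into its error term. If the sequences are unequal, part of it also enters the estimate. No allocation ratio or blocking is stated.

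A separate question is what happens during phase II to an active gain made in phase I. The background (section 3) points in more than one direction: "Since neurofeedback is a learning technique, it has potential for intrinsically lasting effects", and also "This modality could also maximize brain regulation to support efficient brain activity for creation of novel pathways during neurorehabilitation". Section 7c treats durability as something the 5-week visit will answer. Because the estimate is to be carried into a parallel trial, the plan should report something that would show whether the phase I gain faded or grew.

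**Working it through.** **The plan's own figure.** 8 patients a year × 5 years = 40 per diagnosis, 80 in all. This reproduces, but it is accrual arithmetic: the plan gives no effect size, SD, power, alpha or sidedness.

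**Assumptions (none from the documents).** Units are the between-patient SD of CU at one visit. Visit correlation c = 0.8, true effect t = 0.4, two-sided 5% test. Phase I gain exceeds phase II gain by p = 0.25 or 0.5. Visit 18 is the phase II baseline.

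**Paired difference (active minus sham change).**
- Active-first: 2·V18 − V1 − V34, mean t + p if the gain persists.
- Sham-first: V34 + V1 − 2·V18, mean t − p.
- Variance within a sequence: 6(1 − c) = 1.2.

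**1. Equal sequences.** The mean is t with or without adjustment. The SD used by the unadjusted test is √(1.2 + p²), against √1.2 = 1.095 after adjustment. Power and rejection rates are simulated.

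| p | SD, unadjusted | 0.4 / SD | Null rejection, unadjusted | Power N = 80, unadjusted v adjusted | Power n = 40, unadjusted v adjusted |
|---|---|---|---|---|---|
| 0 | 1.095 | 0.365 | 5.0% | equal | equal |
| 0.25 | 1.124 | 0.356 | 4.4% | 89% v 90% | 59% v 61% |
| 0.5 | 1.204 | 0.332 | 3% | 86% v 90% | 54% v 61% |

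**2. Unequal sequences.** With share w randomised to active first, the unadjusted mean shifts by (2w − 1)p.
- 49/31: 18/80 = 0.225, so the shift is 0.06 (p = 0.25) or 0.11 (p = 0.5). Under unblocked 1:1 allocation, a split this uneven or worse has probability 5.7%. Given that split, null rejection is about 7% or 11%, against 5% adjusted.
- 26/14 in a diagnosis group: 12/40 = 0.30, so the shift is 0.08 or 0.15; tail probability 8.1%.
- Over all random splits the shift averages to zero and type I error of the unadjusted test is about 5%.

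**3. Fate of the phase I gain.** Let r be the share of the active gain still present at Visit 34 in active-first patients. Their mean difference becomes t(2 − r) + p, and with equal sequences the overall mean is t(1 + (1 − r)/2).
- r = 1 (full persistence): t, no distortion.
- r = 0.5 (fading): 1.25t = 0.50.
- r = 1.5 (growth): 0.75t = 0.30.

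The documents give no value for r. The shift of 0.10 in the last two cases is below one crossover standard error, √(1.2/80) = 0.122. Period adjustment does not remove it.

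**4. Choice of baseline.** If Visit 1 served both conditions and gains persisted, the mean would be −p2 in active-first and t + p2 in sham-first patients, where p2 is the phase II gain common to both conditions. The average is t/2, half the true effect. Sections 2 and 4a point away from this reading, but 7a does not exclude it.

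**5. Precision of the phase I comparison.** Adjusted for Visit 1, its standard error at N = 80 is √(4(1 − c²)/80) = √0.018 = 0.134, about 10% wider than 0.122.

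**The case against.** A reader might infer that the trial has no protection against order effects or carryover, that false positives are inflated, or that the effect size will be wrong by a known amount. The documents support none of these.

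- Randomised order, the washout and a per-phase baseline are real protections. With Visit 18 as baseline, a gain that persists fully causes no distortion, and lasting effects are what section 3 most directly suggests.
- Type I error over all splits is nominal, and with equal sequences the test errs on the conservative side. The 7% and 11% rates apply only once an uncommon split has occurred.
- Fading and growth are assumptions. The 5-week visit asks whether changes last; it is not evidence that they fade. The remark on novel pathways concerns neurorehabilitation generally, not a later sham phase.
- A 0.5 SD period difference is large: the SD of a change score at c = 0.8 is √0.4 = 0.63, so it is 0.79 of that SD. At 0.25 SD the loss of power is slight.
- The study is described as preliminary, with no data for a power calculation.

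All of this stands and limits the weight of the point. It does not explain omitting a period term, which costs almost nothing, or leaving the phase II baseline unnamed in 7a when the effect size is the trial's stated product.

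**Conclusion.** The point holds as a moderate, inexpensive correction to the analysis. The missing period term costs between 1 and 8 points of power under the assumed values, most of it within diagnosis groups of 40 and at the larger period difference. It also leaves the realised estimate exposed to uneven sequences. It does not inflate overall type I error.

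On carryover, the supportable statement is conditional. If a phase I gain fades during phase II, the crossover effect size would be too large for planning; if it grows, too small. The size cannot be derived from the documents, and the planned analysis would not reveal it. A stronger claim, that carryover will bias this trial, goes beyond the text.

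These results rest on the assumed effect, correlation and period differences, equal correlation between all visits, Visit 18 as phase II baseline, and the hoped-for 80 patients. Fewer patients would lower precision throughout.

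**What to change.** 1. In section 7a, overall and by diagnosis, replace the paired t-test with a period-adjusted crossover analysis: the average of the two sequence means of active-minus-sham change, with within-sequence variance. State which visit is the phase II baseline; on the listed schedule only Visit 18 is available, unless the design figure says otherwise.
2. Report beside it, as a supportive estimate for planning, the randomised phase I comparison: Visit 18 CU by assigned condition, adjusted for Visit 1 CU and diagnosis. Standardise the planning effect by the between-patient SD that matches the next trial's analysis (SD of change, or baseline-adjusted residual SD), not by the SD of paired differences.
3. State that a gap between the two estimates may reflect carryover or a treatment effect that differs between periods, and that it will not be used as a pre-test to choose the analysis. No separate Visit 34 contrast is needed.

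The cost is one degree of freedom, one extra model on data already scheduled, and some wording. Because the phase I estimate is less precise, it supplements the crossover estimate and does not replace it.
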